4.7.2 Handling of Participant Withdrawals or Termination

If patients withdraw from the study, we will remove their information from our REDcap database and we will enroll an additional patient to maintain the recommended sample size.

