5.2.2 Enrollment/Baseline

Enrollment/Baseline Visit (Visit 1, Day 0)

- Obtain informed consent of potential participant verified by signature on study informed consent form.
- Physical exam
- Randomize into treatment cohort or control cohort
- Schedule follow-up visits
- Record VAS, ASES Shoulder and QuickDASH scores.
- Perform Shoulder Series X-Ray

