5.2.3 Intermediate Visits

Intermediate Visits (Week 6, Month 3)

- Follow-up visits
- Record VAS

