6.3 Time Period and Frequency for Event Assessment and Follow-Up

The occurrence of an AE or SAE may come to the attention of study personnel during study visits and interviews of a study participant presenting for medical care, or upon review by a study monitor. All AEs including local and systemic reactions not meeting the criteria for SAEs will be captured on the appropriate RF. Information to be collected includes event description, time of onset, clinician's assessment of severity, relationship to study intervention (assessed only by those with the training and authority to make a diagnosis), and time of resolution/stabilization of the event. All AEs occurring while on study must be documented appropriately regardless of relationship. All AEs will be followed to adequate resolution.

Any medical condition that is present at the time that the participant is screened will be considered as baseline and not reported as an AE. However, if the study participant's condition deteriorates at any time during the study, it will be recorded as an AE. UPs will be recorded in the data collection system throughout the study.

Changes in the severity of an AE will be documented to allow an assessment of the duration of the event at each level of severity to be performed. AEs characterized as intermittent require documentation of onset and duration of each episode.

CONFIDENTIAL

This material is the property of the NYU School of Medicine and Langone Medical Center. Do not disclose or use except as authorized in writing by the study sponsor

The PI will record all reportable events with start dates occurring any time after informed consent is obtained until 7 (for non-serious AEs) or 30 days (for SAEs) after the last day of study participation. At each study visit, the investigator will inquire about the occurrence of AE/SAEs since the last visit. Events will be followed for outcome information until resolution or stabilization.

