8.2 Measures to Minimize Bias

8.2.1 Enrollment/Randomization/Masking Procedures

Patients will be randomized (1:1) using REDCap. The physicians and patients will be blinded to their assigned treatment group.

As each patient receives the barbotage, the patient nor the PI will not know if they are receiving the cortisone in addition to the barbotage. Study team members and [name] will not be blinded and in position to randomize the patients. [name] will not be blinded to the study as she is performing the procedures. [name], the PI, and his patients will be blinded from which combination of the two they receive (barbotage and cortisone or saline/sham).

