8.2.2 Breaking the Study Blind/Participant Code

The study blind for a single patient will be broken if the patient reports severe adverse events. These events will be recorded and then reported to the PI. The information will be confidentially maintained by the PI and study team members. All information will be protected by REDCap.

9 Source Documents and Access to Source Data/Documents

Source data is all information, original records of clinical findings, observations, or other activities in a clinical trial necessary for the reconstruction and evaluation of the trial. Source data are contained in source documents. Examples of these original documents, and data records include: hospital records, clinical and office charts, laboratory notes, memoranda, subjects' diaries or evaluation checklists, pharmacy dispensing records, recorded data from automated instruments, copies or transcriptions certified after verification as being accurate and complete, microfiches, photographic negatives, microfilm or magnetic media, x-rays, subject files, and records kept at the pharmacy, at the laboratories, and at medico-technical departments involved in the clinical trial.

The study case report form (CRF) is the primary data collection instrument for the study. All data requested on the CRF must be recorded. All missing data must be explained. If a space on the CRF is left blank because the procedure was not done or the question was not asked, write "N/D". If the item is not applicable to the individual case, write "N/A". All entries should be printed legibly in black ink. If any entry error has been made, to correct such an error, draw a single straight line through the incorrect entry and enter the correct data above it. All such changes must be initialed and dated. DO NOT ERASE OR WHITE OUT ERRORS. For clarification of illegible or uncertain entries, print the clarification above the item, then initial and date it.

Access to study records will be limited to IRB-approved members of the study team. The investigator will permit study-related monitoring, audits, and inspections by the IRB/EC, the sponsor, government regulatory

CONFIDENTIAL

This material is the property of the NYU School of Medicine and Langone Medical Center. Do not disclose or use except as authorized in writing by the study sponsor

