12.1 Data Collection and Management Responsibilities

Data collection is the responsibility of the clinical trial staff at the site under the supervision of the site PI. The investigator is responsible for ensuring the accuracy, completeness, legibility, and timeliness of the data reported.

All source documents should be completed in a neat, legible manner to ensure accurate interpretation of data. Black ink is required to ensure clarity of reproduced copies. When making changes or corrections,

CONFIDENTIAL

This material is the property of the NYU School of Medicine and Langone Medical Center. Do not disclose or use except as authorized in writing by the study sponsor

cross out the original entry with a single line, and initial and date the change. DO NOT ERASE, OVERWRITE, OR USE CORRECTION FLUID OR TAPE ON THE ORIGINAL.

Copies of the electronic CRF (eCRF) will be provided for use as source documents and maintained for recording data for each participant enrolled in the study. Data reported in the eCRF derived from source documents should be consistent with the source documents or the discrepancies should be explained and captured in a progress note and maintained in the participant's official electronic study record.

Clinical data (including AEs, concomitant medications, and expected adverse reactions data) and clinical laboratory data will be entered into REDCaps. The data system includes password protection and internal quality checks, such as automatic range checks, to identify data that appear inconsistent, incomplete, or inaccurate. Clinical data will be entered directly from the source documents.

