Attachment A

[figure not shown]
Schedule of Events

Activity	Visit 1	Visit 2	Visit 3	Final Session
Study team procedures				
Consent	X			
Medical History	X			
Physical Exam	X	X	X	X
Height	X			
Weight	X			
Vitals signs	X	X	X	X
Randomization	X			
Study intervention provided	X			
Subject Survey	X			X
Shoulder assessments				
QuickDASH	X			X
ASES Shoulder	X			X
VAS	X	X	X	X
Shoulder Radiographs	X			X

[figure not shown]
CONFIDENTIAL

This material is the property of the NYU School of Medicine and Langone Medical Center. Do not disclose or use except as authorized in writing by the study sponsor
Drug/Device Template Version: 13 JUN 2016

Faces rating scale (FRS)

Numerical rating scale (NRS)

CONFIDENTIAL

This material is the property of the NYU School of Medicine and Langone Medical Center. Do not disclose or use except as authorized in writing by the study sponsor

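### Section 4.7.2 deletes withdrawn patients from REDCap and replaces them, so randomised, treated patients leave the comparison along with the data needed to check or reduce the resulting bias

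*Combined protocol and SAP*

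**What the plan says.** Section 4.7.2 gives the rule in one sentence: "If patients withdraw from the study, we will remove their information from our REDcap database and we will enroll an additional patient", the stated aim being to hold the sample size. Section 4.7.1 lets patients withdraw at any time.

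Other sections fix what this means in practice:

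- **Timing.** Section 5.2.2 lists "Randomize into treatment cohort or control cohort" at Visit 1, Day 0. Attachment A marks "Study intervention provided" at Visit 1 only.
- **VAS.** It is recorded at baseline, week 6, month 3 and month 6 (5.2.2 to 5.2.4, Attachment A). The fall in VAS is the primary endpoint (3.2.1).
- **REDCap.** It runs the allocation (8.2.1: "Patients will be randomized (1:1) using REDCap") and holds the trial data (12.1: "Clinical data (including AEs, concomitant medications, and expected adverse reactions data) and clinical laboratory data will be entered into REDCaps").
- **Analysis.** The Protocol Summary and 8.1 name tests only: t tests, ANOVA, Mann-Whitney, chi-squared, Fisher and Pearson's correlation. No section defines an analysis population, a missing-data method or a sensitivity analysis.
- **Other records.** Section 6.3 puts adverse events on report forms ("All AEs including local and systemic reactions not meeting the criteria for SAEs will be captured on the appropriate RF"). Section 9 describes the CRF and source documents, and 12.2 covers retention.
- **Prior data.** Section 11.4 allows continued use of information gathered before a patient revokes authorisation.

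**The concern.** Randomisation makes the two arms comparable as randomised. If patients leave after treatment for reasons connected with how they are doing, those who remain are a selected group. The 6-month VAS difference is then biased whenever the selection differs between arms. A newly enrolled patient does not stand in for the one who left.

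That bias can arise however records are handled. Deletion removes the means of dealing with it. A withdrawn patient's VAS scores up to withdrawal, any adverse events entered in REDCap, and the withdrawal count by arm all leave the trial database. The protocol does not say whether the allocation record goes too. Nobody working from that database could then tell whether withdrawal differed between arms, or adjust for it.

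The direction cannot be predicted. Section 1.3.1 lists pain or inflammation risks both with and without cortisone, and patients are blinded.

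**Working it through.** **The plan's own figure.** Section 8.1 states that more than 128 patients are needed at d=0.6, power 0.80, alpha 0.05. A two-sided, two-sample t test at d=0.6 needs 90 in total; 128 is what d=0.5 needs. That is a separate matter on which this point does not rest, but it is why power is shown below at both values.

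**How many records could go.** If 140 retained patients are wanted, the number randomised is 140/(1−w), rounded up, where w is an assumed withdrawal share.

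| w | Randomised | Removed |
|---|---|---|
| 5% | 148 | 8 |
| 10% | 156 | 16 |
| 14.3% | 164 | 24 |
| 20% | 175 | 35 |

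**Bias from informative withdrawal.** The documents give no withdrawal rate, no arm difference and no link with outcome, so these are assumptions. Let 6-month VAS Y be standard normal (higher is worse). A patient withdraws if U > c, where P(U > c) = p and corr(U, Y) = ρ. With φ the standard normal density and L = φ(c)/(1−p), the retained patients' mean shifts by −ρL and their variance becomes 1 − ρ²(cL + L²). The bias is ρ times the difference in L between arms. Rejection is that of a pooled two-sided 5% t test (noncentral t) with no true difference.

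- p = 10%: c = 1.2816, L = 0.1950.
- p = 5%: c = 1.6449, L = 0.1086.
- p = 10/70 = 14.3%: c = 1.0676, L = 0.2633.

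10% (saline) against 5%: the difference in L is 0.1950 − 0.1086 = 0.0864.

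- ρ = 0.3: 0.3 × 0.0864 = 0.026 SD.
- ρ = 0.5: 0.5 × 0.0864 = 0.043 SD.

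Stress test, 14.3% against 0%. The 10 per group is borrowed from the lost-to-follow-up allowance in 8.1, which is symmetric and is not a withdrawal rate.

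- ρ = 0.3: 0.3 × 0.2633 = 0.079 SD.
- ρ = 0.5: 0.5 × 0.2633 = 0.132 SD.

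| Scenario | ρ | Bias (SD) | Rejection, deleted and replaced (70/70) | Rejection, kept but complete-case |
|---|---|---|---|---|
| 10% v 5% | 0.3 | 0.026 | 5.3% | 5.3% (63/66) |
| 10% v 5% | 0.5 | 0.043 | 5.8% | 5.7% (63/66) |
| 14.3% v 0% | 0.3 | 0.079 | 7.5% | 7.3% (60/70) |
| 14.3% v 0% | 0.5 | 0.132 | 12.4% | 11.8% (60/70) |

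The bias is zero if ρ = 0, or if withdrawal is equally frequent and equally related to outcome in both arms. If saline is truly worse by 0.60 SD, power falls from 0.941 without selection to 0.926 (ρ = 0.3) or 0.921 (ρ = 0.5) at 10% v 5%, and to 0.870 or 0.803 in the stress test.

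**What deletion itself takes away.** This was simulated with four visits, no true difference, an assumed equal between-visit correlation r of 0.5 to 0.7, withdrawal after month 3, and 6,000 trials per setting. The all-visits estimate regresses month 6 on arm, baseline, week 6 and month 3, and predicts at the means of all randomised patients.

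- *Withdrawal follows the recorded 3-month VAS* (r = 0.6). Delete and replace leaves 0.027 to 0.044 SD at 10% v 5%, and 0.079 to 0.131 SD in the stress test. Using all visits brings both to 0.00 SD, with rejection about 5%.
- *Withdrawal follows the unseen 6-month VAS.* Using all visits leaves 0.007 to 0.026 SD at 10% v 5%. In the stress test it leaves 0.030 to 0.087 SD (rejection 5.4% to 8.2%), against 0.078 to 0.134 SD under deletion. Keeping only baseline leaves 0.040 to 0.100 SD (5.5% to 8.9%; 8,000 trials).

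As a rough guide, the share of bias left in the second case is 1 − R². With three earlier visits R² = 3r²/(1+2r), so the share is 0.63 at r = 0.5 and 0.39 at r = 0.7. With baseline alone it is 1 − r², or 0.75 and 0.51.

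**The case against.** The strongest reply is that the harm peculiar to deletion is conditional. Under the tests named in 8.1, keeping the records and testing completers gives almost the same answer (5.3% to 5.7% rejection against 5.3% to 5.8%). The gain appears only if the plan also adopts an analysis that uses the earlier visits. This stands: the missing analysis population is part of the same fault, and both must be repaired together. It does not rescue 4.7.2, because that rule rules out the repair from the trial database.

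Second, the moderate scenario is small, and the larger figures need a one-sided stress test. That is correct, and the case rests on the defect rather than on a demonstrated effect. The model also uses a standardised 6-month score, whereas 3.2.1 speaks of a fall in VAS and a 10% change.

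Third, the data may survive elsewhere. Report forms, the CRF, source documents and retained records could allow reconstruction, so removal from REDCap need not be irreversible. That is fair, but no section says these records would be used to return withdrawn patients to the analysis.

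Some supporting points are weak and carry no weight here. The instruction in section 9 that "All missing data must be explained" is followed by directions for blank CRF items and is mainly about form completion. The section 7 comparison of risks between groups would lose deleted adverse events only if it is run from REDCap, which is not stated. Section 11.4 permits use of prior data but does not require it, and the consent form, a separate document not seen here, may promise deletion.

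**Conclusion.** The concern holds, and 4.7.2 must be changed. It is an explicit rule, not an omission: it takes randomised, treated patients out of the comparison and strips the trial database of the data needed to judge the consequences. Confidence is high in the defect and not in its size, which the documents do not allow anyone to calculate. On the assumptions shown, bias in the primary comparison runs from zero, through 0.03 to 0.04 SD, to 0.08 to 0.13 SD in the stress test. Keeping and using all visits would remove it if withdrawal follows the recorded 3-month score, and only part of it if withdrawal follows the unseen 6-month score. Extra enrolment is not itself the fault; taking the withdrawn patient out of the analysis is. Whether the rule also covers investigator termination is unclear, since the heading names it and the sentence does not.

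**What to change.** Rewrite 4.7.2 and add an analysis-population statement to section 8:

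- Retain everything collected up to withdrawal, including adverse events and the allocation, subject to the consent wording. Say whether termination is covered.
- Invite withdrawn patients to continue outcome follow-up where they agree.
- Analyse all randomised patients in their assigned arm using all available VAS visits. A mixed model on the four visits is one option; the documents do not name it.
- Add a sensitivity analysis that allows worse outcomes in those who withdrew, since the all-visits analysis does not remove all the bias if withdrawal follows the unseen score.
- Report withdrawals and terminations by arm, with reasons.
- Allow extra enrolment only if it does not take a withdrawn patient out of the analysis.

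The cost is a protocol amendment with IRB approval, a check of what the consent form says about data after withdrawal, and possible re-consent. Some records will be incomplete, and fewer than 140 patients may have complete data. At d=0.6, power is 0.94 with 70 per arm and 0.90 with 60. At d=0.5 it is 0.84 with 70 and 0.78 with 60, slightly under the 0.80 target.

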4.7.3 Premature Termination or Suspension of Study

This study may be temporarily suspended or prematurely terminated if there is sufficient reasonable cause. Written notification, documenting the reason for study suspension or termination, will be provided by the suspending or terminating party to investigator. If the study is prematurely terminated or suspended, the PI will promptly inform the IRB and will provide the reason(s) for the termination or suspension.

Circumstances that may warrant termination or suspension include, but are not limited to:

- Determination of unexpected, significant, or unacceptable risk to participants
- Demonstration of efficacy that would warrant stopping
- Insufficient compliance to protocol requirements
- Data that are not sufficiently complete and/or evaluable
- Determination of futility

Study may resume once concerns about safety, protocol compliance, data quality are addressed and satisfy the sponsor and/or IRB.

5 Study Procedures and Schedule

5.1 Study Procedures/Evaluations

Once the study team member arrives to the physician office, they will provide the potential patient subjects with information on the study and ask the patient for their consent to be in the study. The patient will be given shoulder-related questionnaires (ASES and QuickDASH), asked to complete a VAS survey and will receive a shoulder radiograph prior to treatment and at 6 months post-treatment, to evaluate the state of the condition.

Patients in this study will receive the assigned form of treatment and have assigned follow-up appointments at 6 weeks, 3 months and 6 months post-treatment. The alternative treatment (barbotage with saline injection) will be administered in the same fashion as the control (barbotage with cortisone injection). If the patient desired to solely have the standard therapy, they will be ineligible for the study.

Patients will be randomized to one of two cohorts: receiving barbotage with saline injection or receiving barbotage with cortisone injection. Both groups will follow the same protocol for standard of care: 4 mg of dexamethasone (if receiving cortisone) and barbotage. Cortisone dosing is consistent with FDA-approved guidelines. The saline used for the barbotage and sham injection are the same, and readily available in the procedure room. The saline is manufactured by B. Braun Medical, available in the procedural room, and will be equivalent in volume to that of the cortisone injection, determined by the performing physician. [name] will be performing the procedure. At each follow-up appointment, the patients will complete the questionnaires and VAS scores. Patients and physicians will be blinded to the cohort; patients will be randomly chosen by the research study members excluding the primary investigator (PI). The barbotage

CONFIDENTIAL

This material is the property of the NYU School of Medicine and Langone Medical Center. Do not disclose or use except as authorized in writing by the study sponsor

and cortisone/saline (sham) injection will occur concurrently by a different physician from the PI, blinding the PI and patients. The study team members responsible for randomization will converse with the [name], who will be in charge of performing the barbotage and cortisone/saline (sham) procedure. The associated research members and the physician performing the barbotage excluding the PI and patients are the only individuals who will be aware of the blind. Blinding will be maintained until a patient experiences adverse effects, in which case the researchers will inform the primary physician.

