5.2.4 Final Study Visit

Final Study Visit (End of Month 6)

- Record VAS, ASES Shoulder, and QuickDASH scores.
- Perform Shoulder Series X-Ray for Research Purposes

CONFIDENTIAL

This material is the property of the NYU School of Medicine and Langone Medical Center. Do not disclose or use except as authorized in writing by the study sponsor

6 Assessment of Safety

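### Section 5.1 has ASES and QuickDASH completed at every follow-up, but 5.2.3 and Attachment A schedule only VAS at week 6 and month 3; the plan needs one schedule

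*Combined protocol and SAP*

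**What the plan says.** Section 5.1 introduces the instruments separately: "The patient will be given shoulder-related questionnaires (ASES and QuickDASH), asked to complete a VAS survey". It states that patients "have assigned follow-up appointments at 6 weeks, 3 months and 6 months post-treatment", and later adds: "At each follow-up appointment, the patients will complete the questionnaires and VAS scores". Read together, these put ASES and QuickDASH at baseline, week 6, month 3 and month 6.

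Section 5.2 differs. The baseline entry (5.2.2) reads "Record VAS, ASES Shoulder and QuickDASH scores" and the final-visit entry (5.2.4) reads "Record VAS, ASES Shoulder, and QuickDASH scores". Under "Intermediate Visits (Week 6, Month 3") in 5.2.3, VAS is the only score listed. Attachment A agrees with 5.2: the ASES and QuickDASH rows are marked at Visit 1 and the Final Session only, while the VAS row is marked at all four visits.

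Section 3.2.2 makes ASES and QuickDASH the secondary endpoints, judged on change from baseline to the final visit. Section 2.1 also names them in the primary objective. No section says which schedule governs.

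**The concern.** The schedule of events is what clinic staff usually work from. If they follow it, the two function scores will not be taken at week 6 and month 3, and they cannot be recovered afterwards. Section 12.3 counts any noncompliance with the protocol as a deviation, so following Attachment A departs from 5.1 at two visits per patient.

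Two things are at stake. First, early function: section 1.3.1 lists temporary pain and possibly prolonged inflammation as risks of omitting cortisone, so the protocol itself gives a reason to look at the arms early. Second, missing data: with only baseline and month 6, a patient lost in between contributes no post-baseline function score, and section 8.1 names no method for missing values.

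**Working it through.** **Step 1. ASES and QuickDASH, visit by visit**

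| Source | Baseline | Week 6 | Month 3 | Month 6 |
|---|---|---|---|---|
| 5.1 | yes | yes | yes | yes |
| 5.2.2 to 5.2.4 | yes | no | no | yes |
| Attachment A | yes | no | no | yes |

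The columns of Attachment A are matched to the visits by order. Its VAS row has four marks, so the blank cells for the questionnaires are real and not a product of text extraction. The pre/post wording in 5.1.1 settles nothing, because it is used for VAS as well.

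The count is four time points against two. The difference is 2 visits × 140 patients = 280 questionnaire sets before any attrition. That is a count of forms, not an effect on a result.

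**Step 2. Who would gain a post-baseline function score**

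| Patient | Scores under 5.1 | Scores under 5.2 and Attachment A |
|---|---|---|
| Lost before week 6 | 0 | 0 |
| Lost after week 6, before month 3 | 1 | 0 |
| Lost after month 3, before month 6 | 2 | 0 |
| Withdrew (data removed under 4.7.2) | 0 | 0 |

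Only the middle two rows are affected. Section 8.1 limits their number only loosely:

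- 10 extra per group gives 2 × 10 = 20, and 20/140 = 14.3%.
- The target less the stated requirement gives 140 − 128 = 12, and 12/140 = 8.6%.
- The two do not agree, since 128 + 20 = 148, not 140.

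The number affected is therefore some part of 12 to 20.

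**Step 3. Precision for the month-6 comparison**

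The documents give no between-visit correlation, so ρ = 0.3 to 0.7 is assumed. Further assumptions are a score with variance 1, the same ρ between any two visits (compound symmetry), 70 per arm, 60 per arm with a month-6 score, loss at random, and both interim scores present for every lost patient.

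- Complete-case ANCOVA on baseline: V_A = 2(1 − ρ²)/60.
- Longitudinal model using all visits: V_L = 2[(1 − R²)/60 + (R² − ρ²)/70], with R² = 3ρ²/(1 + 2ρ), the share of month-6 variance explained by the three earlier scores.

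| ρ | R² | V_A | V_L | Reduction |
|---|---|---|---|---|
| 0.3 | 0.27/1.6 = 0.16875 | 2 × 0.91/60 = 0.03033 | 2(0.83125/60 + 0.07875/70) = 0.02996 | 1.2% |
| 0.5 | 0.75/2.0 = 0.375 | 2 × 0.75/60 = 0.02500 | 2(0.625/60 + 0.125/70) = 0.02440 | 2.4% |
| 0.7 | 1.47/2.4 = 0.6125 | 2 × 0.51/60 = 0.01700 | 2(0.3875/60 + 0.1225/70) = 0.01642 | 3.4% |

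The gain is about 1% to 3%. This is a favourable case: a smaller loss, loss before both interim visits, or deletion under 4.7.2 would all reduce it. The plan states no figure of its own on this point to reproduce.

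**The case against.** The strongest reply is that the two-time-point schedule was intended and that one loose sentence in 5.1 is the outlier. Sections 5.2.2 to 5.2.4 and Attachment A agree with each other, and the endpoint in 3.2.2 runs from baseline to the final visit. Section 5.1 is itself mixed: the sentence introducing the instruments ends by saying that the patient "will receive a shoulder radiograph prior to treatment and at 6 months post-treatment", and that timing could be read as covering the whole list. On this view, correcting 5.1 ends the conflict at no burden to patients, and nothing planned is lost, because no analysis in 8.1 uses interim function scores.

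Much of this stands. The documents do not show which schedule was meant, and amending 5.1 is a legitimate way out. It does not remove the contradiction, though. If the timing phrase covered the whole list, it would also confine VAS to baseline and month 6, which 5.2.3 contradicts. The later sentence in 5.1 says each follow-up without qualification.

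A reader might also infer that up to 20 of 140 patients would lose a function score because of the conflict, or that any early effect of cortisone would go unmeasured. The documents support neither. The allowance may be 12, patients lost before week 6 gain nothing from interim forms, and withdrawn patients' data are removed in any case. VAS pain, which 3.2.1 makes a primary endpoint, is recorded at week 6 and month 3 in both 5.2.3 and Attachment A.

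**Conclusion.** The inconsistency is real: four function assessments under 5.1, two under 5.2 and Attachment A, with nothing to say which applies. It decides whether secondary-endpoint data that 5.1 promises will exist.

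Its reach is limited. VAS and the baseline-to-month-6 comparison of ASES and QuickDASH can be analysed under either schedule. The loss is confined to early function and to interim scores for patients lost to follow-up, without withdrawing, between week 6 and month 6. The 1% to 3% variance gain rests on the assumed correlations and on every lost patient having both interim scores. Interim scores may help more if loss depends on earlier function, but that benefit is not quantified here and the documents give no basis for a figure. It would go too far to infer that the function endpoint is compromised. This is an internal inconsistency of minor to moderate severity.

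**What to change.** State one ASES and QuickDASH schedule in 5.1, 5.2.3 and Attachment A.

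- **Preferred:** mark both questionnaires at Visits 2 and 3 in Attachment A, add them to 5.2.3 as 5.1 already states, and analyse the month-6 score with a baseline-adjusted repeated-measures model using all visits. The cost is two short self-completed forms at visits that already take place, a few minutes of patient time, and an edit to the schedule and to 8.1.
- **Alternative, if only baseline and month 6 were intended:** correct the follow-up sentence in 5.1 and specify a baseline-adjusted (ANCOVA) comparison of the month-6 scores. This costs only text, but gives up early function data.

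Either model would replace, for these endpoints, the paired t-tests or Mann-Whitney tests named in 8.1, neither of which is a baseline-adjusted comparison between arms. Interim scores are no remedy for patients whose data are removed under 4.7.2.
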